Official Title: The Effect of Dental Anxiety on the Success of Mandibular Anesthesia in Mandibular Molar Teeth with Symptomatic Irreversible Pulpitis: A Prospective Clinical Study

NCT Number: Not available

Date: 15/12/2024

Null Hypothesis (H₀): Dental anxiety does not affect the success of mandibular anesthesia in the treatment of symptomatic irreversible pulpitis in mandibular molar teeth.

Study arms: A prospective clinical trial with two parallel intervention arms. Participants will be divided into two groups based on their Modified Dental Anxiety Scale (MDAS) scores:

- Group 1 (Low Anxiety Group): MDAS score < 10
- Group 2 (Moderate to High Anxiety Group): MDAS score ≥ 11 (including those with dental phobia if MDAS > 19)

Sample Size Calculation: Using G*Power 3.1.9.7 software, based on an effect size of 0.8, $\alpha = 0.05$, and power = 0.80, the required sample size was determined as **26 patients per group**, totaling **52 participants**. The actual power achieved was 81%.

Materials and Methods:

Inclusion Criteria:

- Systemically healthy adults aged 18–65
- Mandibular molar teeth with symptomatic irreversible pulpitis requiring root canal treatment
- Radiographic evidence of closed apex and absence of periapical pathology
- Periodontal probing depth ≤ 3 mm
- Tooth mobility < 0.5 mm
- Pain score of 55–170 mm on the Heft-Parker Visual Analog Scale (HP-VAS) (i.e., moderate or severe pain)
-

• Exclusion Criteria:

- Systemic disease
- Teeth with open apex, periapical lesion, internal or external resorption
- Periodontal probing depth > 3 mm
- Tooth mobility > 0.5 mm
- HP-VAS score < 55 mm (no or mild pain)
- Pregnant patients or those with allergy to articaine

Procedure:

- All treatments and measurements will be conducted between 09:00 and 12:00 to minimize circadian and cortisol fluctuations.
- Patients will avoid food intake for at least 2 hours before treatment and abstain from caffeine, alcohol, tobacco, and intense exercise within 24 hours.
- Patients will rest in the dental chair for 5 minutes, then their demographic data will be recorded.
- MDAS will be administered to assess anxiety level.
- HP-VAS will be used to assess pre-treatment pain level.
- Pulse rate, SpO₂, and salivary cortisol levels will be recorded pre- and post-anesthesia.

Anesthesia Protocol:

- All procedures are performed by a single operator in a one-unit room.
- Topical anesthesia: 10% lidocaine spray (Locanest) applied for 60 seconds.

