- IANB (Inferior Alveolar Nerve Block):
 - 1.8 ml of 4% articaine hydrochloride with 1:100,000 epinephrine (Ultracaine DS Forte) via 27G needle
- Buccal and lingual infiltration:
 - Additional 1.8 ml injection performed 5 minutes after IANB
- Block Failure Definition:
 - If deep lip numbness is not achieved within 15 minutes, the block is considered failed and the participant is withdrawn from the study.

Outcome Evaluation:

- During treatment, if the patient feels pain, they raise their hand, and the pain is marked on the HP-VAS.
- If required, supplemental anesthesia (PDL or intrapulpal) will be administered and recorded.
- Successful anesthesia: No or mild discomfort
- Failed anesthesia: Moderate or severe pain
- Cold test will be performed 15 minutes after IANB. If positive, additional anesthesia will be given.

Biological Sampling:

- Saliva samples will be collected 15 minutes before and after anesthesia.
- Samples will be stored at -80°C until analysis.
- Special sterile, single-use Sali-Tubes (SLV-4158, DRG, Germany) will be used.

Statistical Analysis:

All statistical analyses will be performed using SPSS Statistics 20 software (IBM Corp., Armonk, NY) at a 5% significance level. If the data are normally distributed, Student's t-test will be used to compare preoperative pain levels, salivary cortisol, SpO₂, and pulse rate across different anxiety levels. Chi-square test will be used to analyze the relationship between anxiety levels and the success rate of anesthesia.

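### Student's equal-variance t-test is named for MDAS-defined groups whose final sizes are not protected; Welch's test would hold the 5% level at almost no cost (minor)

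*Combined protocol and SAP*

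**What the plan says.** - **Test.** The Statistical Analysis section states that "Student's t-test will be used to compare preoperative pain levels". The same sentence applies the test to cortisol in saliva, oxygen saturation and pulse, and all testing is "at a 5% significance level". Normality is the only condition. No unequal-variance version is named.
- **Groups.** Under Study arms, "Participants will be divided into two groups based on their Modified Dental Anxiety Scale (MDAS) scores". Group 1 is MDAS below 10. Group 2 is MDAS 11 or more, "including those with dental phobia if MDAS > 19".
- **Sizes.** The Sample Size Calculation sets 26 per group, 52 in total. It does not say that recruitment continues until each group reaches 26.
- **Losses.** Under Anesthesia Protocol, Block Failure Definition, if lip numbness is not achieved within 15 minutes "the block is considered failed and the participant is withdrawn from the study". No replacement rule or loss allowance is given.
- **Main hypothesis.** It is tested differently: "Chi-square test will be used to analyze the relationship between anxiety levels and the success rate of anesthesia".

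**The concern.** Student's test pools the two group variances. With unequal spreads its level is close to nominal only when the group sizes are about equal. If the more variable group is the smaller one, the pooled standard error is too small, which gives too many false positives and intervals that are too narrow. If the more variable group is the larger one, the test is conservative.

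Neither protection is guaranteed here. The groups are observed, so random allocation does not make their spreads alike under the null. The final sizes depend on withdrawals after grouping and on a per-group target with no rule for filling it. The study asks whether anxiety affects the success of the block, so unequal losses between groups cannot be ruled out. At stake is the stated 5% level for four physiological and pain comparisons.

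**Working it through.** **1. The plan's own figure.** The inputs are effect size 0.8, α = 0.05, power 0.80 and 26 per group (Sample Size Calculation). Reading the effect size as a standardised mean difference in a two-sided, equal-variance t-test (type and sidedness are not stated), the noncentrality is 0.8 × √(26 × 26 / 52) = 2.88 on 50 df. The exact power is 80.7%; with 25 per group it is 79.1%. So 26 per group and 81% both reproduce.

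**2. Why balance matters.** Let k be the true variance of the mean difference divided by the variance that Student's test estimates on average:

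k = (s₁²/n₁ + s₂²/n₂) / [sₚ²(1/n₁ + 1/n₂)], with sₚ² = [(n₁−1)s₁² + (n₂−1)s₂²] / (n₁+n₂−2).

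In the cases below, s₁ = 1 and s₂ = 2 (assumed), with Group 1 listed first.

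- 26/26: sₚ² is the simple average of the variances, so k = 1 whatever the SDs.
- 26/20: true variance 1/26 + 4/20 = 0.2385. Pooled: (25 + 76)/44 = 2.295, times (1/26 + 1/20) = 0.0885, gives 0.2031. So k = 1.17. The critical value 2.015 acts as 2.015/√1.17 = 1.86, an error of about 7.0%.
- 20/26: true variance 1/20 + 4/26 = 0.2038. Pooled: (19 + 100)/44 = 2.705, times 0.0885, gives 0.2392. So k = 0.85. The effective critical value is 2.18, an error of about 3.4%.

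**3. Simulation.** Normal data, no true difference, 200,000 runs per cell for splits up to 34/18 (simulation error about 0.05 point) and 400,000 for 36/16. The SD ratio is Group 2 over Group 1. Ratios and unequal splits are assumptions.

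| Split (Group 1/Group 2) | Student, ratio 1.5 | Student, ratio 2 | Welch, both ratios |
|---|---|---|---|
| 26/26 (planned) | 5.0% | 5.2% | 4.9–5.0% |
| 26/23 | 5.7% | 6.1% | 5.0% |
| 26/20 | 6.3% | 7.3% | 5.0% |
| 20/26 | 4.0% | 3.6% | 5.0% |
| 34/18 | 8.2% | 10.7% | 5.0–5.1% |
| 18/34 | 2.8% | 2.0% | 4.9–5.0% |
| 36/16 | 9.1% | 12.4% | 5.0% |

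At ratio 3 Student's error is 5.3% at 26/26, 8.2% at 26/20 and 3.3% at 20/26. With equal SDs it is about 5% at every split tested.

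**4. Which splits follow from the plan.** The 34/18, 18/34 and 36/16 splits each total 52, so they contain no withdrawals. They would arise only if the per-group target were not enforced. Withdrawal from 26/26 gives splits such as 26/23, or 26/20 if 6 of 26 patients (23%) were lost from one group and none from the other.

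**5. How far pooling anxiety bands alone widens spread.** Assume scores 5–9 and 11–25, evenly spread, a linear effect of score on outcome, and residual SD 1. Score variances are (5² − 1)/12 = 2 and (15² − 1)/12 = 18.67; means are 7 and 18. A group difference of 0.8 SD gives a slope of 0.8/11 = 0.0727. The SD ratio is √[(1 + 0.0727² × 18.67)/(1 + 0.0727² × 2)] = √(1.099/1.011) = 1.04. With a 1.2 SD difference it is 1.09. At ratio 1.04 Student's error is 5.1% at 26/20 and 5.4% at 36/16.

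**6. Power cost of Welch** (equal SDs, difference 0.8 SD, Student v Welch, simulated): 26/26, 80.7% v 80.6%, a loss of under 0.1 point; 26/20, 74.9% v 74.7%, a loss of 0.2–0.3 point; 36/16, 74.4% v 73.0%, a loss of about 1.4 points.

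**The case against.** The strongest case for leaving the text alone has five parts.

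- *The plan targets equal groups.* MDAS decides which group a patient joins, not how large the group is meant to be. At 26/26 Student's test is sound. This stands, and it limits the point to departures from the target.
- *The large error rates come from splits that the plan does not predict.* A reader might infer from the 34/18 or 36/16 rows that the trial's error rate will be far from 5%. The documents do not support that: withdrawal does not produce such splits, and nothing says that the 1:1 target will be abandoned. This stands.
- *SD ratios of 1.5–2 are not in the documents.* Pooling moderate, high and phobic patients widens spread only if the outcome varies with anxiety, and then the group means would generally differ as well. On that route alone the ratio is about 1.04. Preoperative pain is also limited to 55–170 mm in both groups. This stands as a limit on how likely the harm is. It does not exclude unequal spread for other reasons, such as more variable cortisol or pulse responses among anxious patients.
- *The affected comparisons do not test the stated hypothesis.* Anesthesia success is tested by chi-square. This stands; a reader should not infer that the main conclusion is at risk.
- *Welch is not free when groups are very unequal.* With equal SDs it loses about 2–3 points of power at 14/38 or 12/40. True, but those splits are further still from the plan.

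What remains is that the plan gives no assurance of equal spread or equal final size, and a near-costless wording removes the dependence on both.

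**Conclusion.** The point holds as a minor, cheap improvement. At the planned 26/26 there is no material problem. If losses left the groups at 26 and 20, and if SDs differed by a factor of 1.5–2, Student's error would be about 6.3–7.3% or 3.6–4.0%, depending on which group is more variable; Welch's would be about 5%. This rests on normal data, on SD ratios that the documents neither give nor exclude, and on an imbalance that the documents permit but do not predict. It concerns preoperative pain, salivary cortisol, SpO₂ and pulse rate only.

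**What to change.** In the Statistical Analysis section, keep the normality condition and replace Student's t-test with Welch's unequal-variance t-test for these four between-group comparisons. Take each confidence interval from the same test. Do not choose between the two tests by a preliminary variance test.

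It would also help to state in the sample size section whether each group is recruited until it reaches 26 and whether withdrawn patients are replaced, since that is where any imbalance would come from.

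The test change is a single wording edit and needs no extra patients or data. Its price is the power loss in step 6 of the working: negligible at or near the planned split.
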